2.2. Secondary Objectives

The secondary objectives of this study are:

- To assess the proportion of women who achieve high adherence early (month 2).
- To evaluate the optimal sequence of intensifying adherence support among young women who have low adherence after the first two months of use.

- To identify correlates of PrEP adherence, after adjusting for study arm, such as adherence at prior study visits, sociodemographic factors, individual-level and partner-level characteristics, exposure to study-based adherence support, and risk practices.
- To assess the proportion of young women who discontinue PrEP, timing of discontinuation, and factors associated with PrEP discontinuation.
- To characterize SMS response rates and the content and frequency of use of WhatsApp groups
- To qualitatively explore factors that influence women's decisions to use PrEP and adhere to PrEP and their satisfaction with their assigned intervention(s).
- To qualitatively explore perceptions of our intervention package and opinions on scalability of the interventions from clinic staff and key informants' perspectives.

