4.2.4. Month 3 randomization visit

Women with high adherence (i.e., TVF-DP ≥ 500 fmol/punch based on Month 2 drug levels) who have not missed PrEP refills at Month 1 or 2 will be considered ‘responders’. Responders will move to quarterly visits and continue to be offered the adherence support they were randomized to at enrollment. Pharmacy refills will be verified using electronic pharmacy records.

‘Non-responders’ (i.e., TFV-DP < 500 fmol/punch or missed PrEP refill) will be randomized to a more intensive adherence support – continued monthly counseling visits or quarterly visits with counseling based on drug levels at months 3 and 6. Randomization will be conducted with a ratio of 1:1 between the two study arms. We will use envelopes in order to assign “non-responding” subjects to the second intervention. Envelopes will be prepared by study staff in Seattle and site staff in Johannesburg will open the envelopes in the specified order only when they are ready to randomize a “non-responding” participant.

All women will continue with the intervention they were assigned in their initial randomization (WhatsApp groups or two-way SMS) regardless of if they are classified as responders or non-responders. Additional month 3 visit procedures are included in section 4.2.5.

[figure not shown]
In the case of public health emergencies, study procedures that require in person visits may be delayed, including blood draws to determine secondary randomization. Therefore, secondary randomization may be conducted using blood drawn from visits occurring between months 1 and 3.

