6.3. Accrual, Follow-up, and Sample Size

For the SMART trial design, the goal is to enroll and randomize up to 500 women in order to achieve an analysis sample size of approximately 350 women who return for their one-month study visit and will want to continue PrEP for a further 9 months: 175 per arm randomized into the first intervention at enrollment, continuing past their 1-month study visit and evaluable at 9 months. Up to 500 women who initiate PrEP will be enrolled over a period of approximately 18 months. 350 evaluable women

would have 96% power for the initial randomization to detect an increase from 40% response at 2 months to SOC + two-way SMS to 60% with the SOC + WhatsApp groups. Among the estimated 70-105 non-responders in each initial group, we have 79-96% power in each group of non-responders to detect a 30% difference in adherence at 9 months between women randomized to monthly counseling or drug level feedback. Pooling across the initial randomization, with 149-166 women we would have ~80% power to detect ~ 15-20% difference (Table 2).

Table 2: Power to assess differences in adherence by intervention strategies in each of the first and second stages using a one-sided $\alpha = 0.025$.

First Randomization			Second randomization (Pooled across first randomization)			
% Adherent				% Adherent		
WhatsApp + SOC N = 175	SMS + SOC N = 175	Power	Non-responders Total N	Monthly visits	Drug Level Counseling	Power
65%	40%	99%	166	40%	25%	84%
				50%	30%	89%
60%	40%	96%	175	40%	25%	86%
				50%	30%	91%
55%	40%	84%	184	40%	25%	88%
				50%	30%	91%

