At month 3, women who have TFV-DP <500 fmol/punch (based on a blood sample collected at month 2) or who miss PrEP refills at the month 1 or 2 visits will undergo a secondary 1:1 randomization to either continue monthly follow-up visits with problem-focused counseling until month 8 or attend quarterly visits with drug level feedback counseling at months 3 and 6. Women will also continue to receive the adherence support from their original randomization (i.e., WhatsApp groups or weekly two-way SMS).

Women who have TFV-DP ≥ 500 fmol/punch at month 3 (based on a blood sample collected at month 2) will continue to receive the adherence support in their original randomization (SOC adherence counseling, one-way SMS reminder messages, and either WhatsApp groups or weekly two-way SMS) with quarterly visits. **Table 1** depicts the four embedded dynamic treatment strategies and decision rules for determining non-adherence and re-randomizing women at their month 3 visit:

Table 1. Embedded dynamic treatment strategies and corresponding decision rules

Dynamic treatment strategy	Decision rule
Non-response definition: TFV-DP levels <500 fmol/punch or missed refills	
First, offer monthly SOC counseling and WhatsApp group intervention; then add drug level feedback with quarterly visits for non-responders and switch responders to quarterly SOC visits and continued WhatsApp groups	First-stage intervention option = {SOC + WhatsApp} IF evaluation = {non-response} THEN second-stage intervention option = {DLFB + first-stage intervention option + quarterly study visits}

	ELSE continue on first-stage intervention option + quarterly study visits
First, offer monthly SOC counseling and weekly two-way SMS intervention; then add drug level feedback with quarterly visits for non-responders and switch responders to quarterly SOC visits and continued weekly two-way SMS	
First-stage intervention option = {SOC + SMS}
 
IF evaluation = {non-response}
 
THEN second-stage intervention option = {DLFB + first-stage intervention option + quarterly study visits}
 
ELSE continue on first-stage intervention option + quarterly study visits

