    estimate 'DTS1' int 1 X1 0 X2 0 X1*X2 0 / exp;
    estimate 'DTS2' int 1 X1 0 X2 1 X1*X2 0 / exp;
    estimate 'DTS3' int 1 X1 1 X2 0 X1*X2 0 / exp;
    estimate 'DTS4' int 1 X1 1 X2 1 X1*X2 1 / exp;
    contrast 'globalnull' X1 1,
                        X2 1,
                        X1*X2 1 / e;

run;

```

- The 'estimate' statements will provide estimates of the probability of adherence (response) for each of the 4 embedded DTS, along with 95% CIs.
- The 'contrast' statement is a test of the global null hypothesis that the 4 embedded DTS are equal. The 'e' option will produce the contrast matrix, which should be checked to ensure the appropriate test is being done.

- 2) We will also include inverse probability weights to account for censoring if overall loss to follow-up in the full sample is >10% by month 9 or if differential loss to follow-up between the two arms is >10%.
- 3) Secondary analysis: We will conduct a modified intent-to-treat analysis using the same procedures described above (i.e., the weighted and replicated approach) but restricting to participants who returned for at least one study visit between months 1 and 3.
 - Since this analysis breaks randomization, we will adjust for important prognostic variables (including demographics, sexual behavior factors, and HIV risk factors) to account for treatment imbalances.

Secondary Analysis 1: Evaluate (1) the effect of the mHealth interventions on early PrEP adherence (month 2), (2) the effect of the mHealth interventions on long-term PrEP adherence (month 12) and (3) the effect of the additional adherence support interventions (second-line interventions) on long-term PrEP adherence (month 12) separately for (a) non-responders to the first-line SMS intervention and (b) non-responders to the first-line WhatsApp intervention

Analysis population:

- All individuals randomized to two-way SMS or WhatsApp groups who have drug levels available at month 2 and/or month 12.

- All individuals randomized to either monthly counseling or drug-level feedback who had drug levels available at month 12.

Outcome: PrEP adherence at the 2- and 12-month study visits, defined as a binary outcome variable around TFV-DP levels of 700 fmol/punch

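### SAP Secondary Analysis 1 compares early adherence only among women with a month-2 drug level, so it omits women who never returned and does not estimate the proportion of all women randomized

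*SAP*

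**What the plan says.** Protocol 2.2 gives the early objective as "To assess the proportion of women who achieve high adherence early (month 2". Protocol 6.2.2 and SAP Secondary Analysis 1 agree on the endpoint: month-2 TFV-DP dichotomized at 700 fmol/punch, with no refill component. The SAP population for the SMS versus WhatsApp comparison is "All individuals randomized to two-way SMS or WhatsApp groups who have drug levels available at month 2 and/or month 12". In practice a woman enters the month-2 comparison only if she has a month-2 level. Neither document says how an absent month-2 level is scored.

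The month-9 intent-to-treat analysis (SAP Primary Analysis 1) instead names all randomized participants. Secondary Analysis 1 borrows the methods of Primary Analyses 1 and 2. These include inverse-probability weighting as a sensitivity analysis, used if overall loss exceeds 10% by month 9 or if loss differs by more than 10% between arms.

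The rule for re-randomization is separate. Women with TFV-DP below 500 fmol/punch "or who miss PrEP refills at the month 1 or 2 visits will undergo a secondary 1:1 randomization" (SAP, Study Design). On refill data, Protocol 4.2.4 states: "Pharmacy refills will be verified using electronic pharmacy records".

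**The concern.** Whether a level exists is decided after randomization, and it is tied to the outcome. The month-2 blood spot and the month-2 refill belong to the same visit (Protocol 4.2.3), so a woman who stopped coming normally has neither. Early loss is expected to be large: Protocol 6.3 randomizes up to 500 to obtain "approximately 350 women who return for their one-month study visit" and wish to continue, and Protocol 6.4.1 expects high drop-out before month 1.

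The arms could also differ in who returns. A missed or negative SMS reply leads to a staff call within 24 hours (Protocol 4.2.1.3), while WhatsApp relies on moderated peer groups (4.2.1.2). If one arm brings back more women who are struggling with pill-taking, that arm's proportion falls because its denominator grows. At stake are the level of early adherence reported and, under some conditions, the comparison of the first-line arms.

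**Working it through.** **1. The plan's own month-2 figure.** Protocol 6.3 states that its evaluable sample "would have 96% power for the initial randomization to detect an increase from 40% response at 2 months"; the 40% is for the SMS arm, and the alternative is 60% in the WhatsApp arm. Inputs: 175 per arm, 40% vs 60%, one-sided 0.025.

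Power = Φ{[0.20 − 1.96·√(2·0.5·0.5/175)] / √[(0.4·0.6 + 0.6·0.4)/175]} = Φ{(0.20 − 0.1048)/0.0524} = Φ(1.82) = 96.6%.

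The stated 96% is reproduced. It applies to evaluable women.

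**2. Tablet supply.** Enrollment dispenses one bottle (Protocol 4.2.1) of 30 tablets (4.4.1). Protocol 1.2.1 equates 700 fmol/punch with four or more doses a week.

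- No refill since enrollment: 30 tablets / 60 days × 7 = 3.5 a week at most, on average.
- Month-1 refill collected, month-2 visit missed: 60 / 60 × 7 = 7 a week available. Nothing can be presumed.

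The 3.5 is an average. A woman who started late could concentrate her tablets: 30 over 42 days is 5 a week. The first bullet is thus a strong presumption, not proof. Protocol 1.2.1 also reports 92% specificity for the 700 cut-off (95% CI 81–100%), so about 8% of women taking fewer than four doses a week would exceed it.

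**3. Effect on the reported proportion.** Let m be the share without a level and q the share of them at or above 700. Then p(all) = p(observed)·(1 − m) + q·m. The documents give no month-2 figure for m. The 30% used here is borrowed from 500 randomized and 350 evaluable, (500 − 350)/500.

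- q = 0: 40% becomes 0.40 × 0.70 = 28%; 60% becomes 42%.
- q = 8%: 40% becomes 28% + 0.08 × 0.30 = 30.4%.
- q = 20%: 40% becomes 34%; 60% becomes 48%.
- m = 10% and q = 0: 40% becomes 36%.

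With equal m and q = 0 the relative risk stays at 1.5 (42/28).

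**4. Effect on the arm contrast, no true difference.** Attendance splits are assumptions; 250 per arm is half of 500.

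*Case A: every non-attender non-adherent, 28% of randomized women adherent in both arms.* At 75% vs 65% attendance the observed proportions are 0.28/0.75 = 37.3% and 0.28/0.65 = 43.1%. The pooled value is 40%, and SE = √[0.24·(1/187.5 + 1/162.5)] = 0.0525, so z = 0.0574/0.0525 = 1.09. The chance of two-sided p < 0.05 is Φ(1.09 − 1.96) + Φ(−1.09 − 1.96) ≈ 19%.

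*Case B: 40% adherent regardless of attendance.* Scoring every absent level as failure gives 0.40 × 0.75 = 30% and 0.40 × 0.65 = 26%. SE = √(0.28·0.72·2/250) = 0.0402 and z = 1.00, so the rejection rate is about 17%.

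| Attendance | Case A, levels-available analysis | Case B, absent = failure |
|---|---|---|
| 72.5% / 67.5% | 8.5% | 8% |
| 75% / 65% | 19% | 17% |
| 80% / 60% | 60% | 51% |

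In Case A, scoring all randomized women holds about 5%; in Case B, the levels-available analysis does. Each follows from its assumption. Between the extremes, with 10% of women without a level adherent, Case A at 75/65 gives 11%. At 175 per arm (the SAP's 350 randomized), Case A at 75/65 gives 15%.

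**5. Power if everyone without a level were scored as failure.** At m = 30%, 28% vs 42% gives 91% power with 250 per arm and 79% with 175 per arm.

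**The case against.** A reader might infer that the plan contradicts itself by defining month-2 response in two ways. It does not. The 500-or-missed-refill rule decides who is re-randomized, and the 700 endpoint measures effect. Protocol 6.1 separates the two thresholds and the SAP keeps the 700 endpoint. A reader might also infer that early adherence is overstated relative to the design's responder rate. That cannot be shown: the stricter 700 cut-off pushes the other way. A woman who missed her month-1 refill but has a month-2 level is kept and classified by that level.

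It is fair to say that the plan has some protection. The inherited weighting would be triggered at a 30% overall loss, Protocol 6.4.1 adjusts for confounders of month-1 drop-out, and Protocol 6.4.2 reweights if loss depends on covariates. These are partial. The SAP weighting is a sensitivity analysis whose overall-loss trigger is read at month 9, and weighting on measured covariates does not use what the tablet supply shows.

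The strongest objection is to blanket failure scoring, and it stands. Protocol 4.2.4 and 4.2.7 allow delayed blood draws, remote visits and home delivery, so an absent level need not mean non-adherence, and Case B shows the harm. The 30% is also borrowed: no month-2 attendance is stated, and the SAP plans about 350 randomized rather than up to 500.

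**Conclusion.** The concern holds in a limited form. The month-2 comparison conditions on a post-randomization event and removes women whose supply makes high adherence unlikely. At the same 700 cut-off, the reported proportion exceeds the all-randomized proportion whenever women without a level are less adherent than those with one; 40% against 28% is the case of 30% without a level and none adherent.

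Bias in the arm contrast is conditional. It needs availability to differ by arm and women without a level to be mostly non-adherent. The 19% type I error illustrates that case; it is not a forecast. With equal availability and none of the women without a level adherent, the relative risk is unaffected. The point concerns one secondary endpoint and should be corrected, but it does not touch the month-9 primary analysis.

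**What to change.** In SAP Secondary Analysis 1:

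- Set the month-2 population to all randomized women.
- Score as not adherent those with no month-2 level and no PrEP refill, collected or delivered, since enrollment.
- Treat every other absent level as missing (month-1 refill received, or an assay, remote-visit or delayed-visit reason), with inverse-probability weighting triggered on month-2 rather than month-9 loss.
- Add a sensitivity analysis that scores women who missed only the month-2 refill as not adherent.
- Keep the levels-available comparison as supportive, and report level availability by arm.

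The cost is SAP wording and a little more analysis, using refill records that the site already plans to verify. Reported month-2 proportions will be somewhat lower. Some power may be lost, though less than in step 5, because only women with no refill are scored as failures.

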Study Duration:	Approximately 48 months, including submissions to Institutional Review Boards (IRBs) and the South African Health Products Regulatory Authority (SAHPRA, formerly the Medicines Control Council), recruitment, and 9 months of follow-up per participant.
Primary Objective:	To evaluate the proportion of young South African women who adhere well to PrEP with regular clinic visits and mHealth interventions alone, the proportion of women who adhere well to PrEP with intensified interventions (i.e. monthly visits and special issue counseling or quarterly visits with drug-level feedback about recent adherence), and the optimal

	sequence of intensifying adherence support among young women who have low adherence after the first two months of use.
Secondary Objectives:	
 • To assess the proportion who achieve high adherence early (month 2). • To assess the correlates of PrEP adherence, after adjusting for study arm, including adherence at prior study visits, sociodemographic factors, individual-level and partner-level characteristics, use of adherence support, and risk practices. • To assess the proportion of young women who discontinue PrEP, timing of discontinuation, and factors associated with PrEP discontinuation. • To characterize SMS response rates and the content and frequency of use of WhatsApp groups. • To qualitatively explore factors that influence women's decisions to use PrEP and adhere to PrEP and their satisfaction/preferences for with their assigned intervention(s). • To qualitatively explore perceptions of our intervention package and opinions on scalability of the interventions from clinic staff and key informants' perspectives.
Exploratory Objectives:	
 • To assess HIV incidence and to assess the association with detectable TFV-DP in PrEP users who acquire HIV infection during the study. • To describe antiretroviral (ARV) drug resistance among women who acquire HIV infection. • To assess acceptability and feasibility of a urine point-of-care test for drug-level feedback counseling.
Study Site:	Ward 21 CRS, Wits RHI, University of the Witwatersrand, in Johannesburg, South Africa.

OVERVIEW OF STUDY DESIGN

Figure 1. Study schema for a stepped PrEP adherence support intervention

PrEP SMART Design Study Schema

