6.4.2. Secondary Analyses

The primary analyses will be repeated to assess the intervention effects on dried blood spot drug concentrations above 700 fmol/punch at 2 months. Given the long half-life for TFV-DP, gradients of cumulative adherence can also be estimated, such as those described in iPrEX OLE as follows: Below limit of quantitation (BLQ, no doses), BLQ to 349 fmol/punch (fewer than two tablets per week), 350–699 fmol/punch (two or three tablets per week), 700–1249 fmol/punch (four to six tablets per week), and ≥ 1250 fmol/punch (daily dosing). We will also assess the intervention effects on continuously measured TFV-DP concentrations (measured in dried blood spots) Months 2 and 9.

The correlates of response (PrEP adherence based on drug levels) at 2 and 9 months will be assessed using logistic regression modelling, evaluating demographic, behavioral, perceived risk, stigma, self-efficacy, relationship power, transactional sex, IPV, and alcohol use and PrEP adherence by intervention strategy. We will also assess whether level of engagement with the primary intervention (WhatsApp and SMS) is a mediator in the pathway between intervention assignment and PrEP drug levels at Months 2 and 9.

Survival analysis will be used to assess the effect of the adherence strategies as well as individual characteristics (demographics, etc.) on time to PrEP discontinuation for those who choose to stop PrEP before 9 months.

Sensitivity analyses will be performed to assess whether loss-to-follow up is covariate-dependent, and if so, all analyses will be rerun using weighting to account for potentially informative drop-out. Secondary analyses will also explore the possibility of a WhatsApp peer group effect, as young women interacting with one another through the intervention may exhibit correlated outcomes.

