- To evaluate (1) the effect of the mHealth interventions on early PrEP adherence (month 2), (2) the effect of the mHealth interventions on long-term PrEP adherence (month 12), and (3) the effect of the additional adherence support interventions on long-term PrEP adherence (month 12) among (a) non-responders to the first-line SMS intervention and (b) non-responders to the first-line WhatsApp intervention.
- To identify correlates of PrEP adherence at the two-, nine- and twelve-month study visits, adjusting for study arm, such as sociodemographic factors, individual-level and partner-level characteristics, and risk practices.
- To assess the proportion of young women who discontinue PrEP, timing of discontinuation, and factors associated with PrEP discontinuation, adjusting for study arm.
- To characterize SMS response rates and the content and frequency of use of WhatsApp groups
- To qualitatively explore factors that influence women's decisions to use PrEP, adhere to PrEP, and their satisfaction with their assigned intervention(s) and preferences for another intervention option.

The exploratory objectives of this study are:

- To assess HIV incidence and the presence of detectable TFV-DP in PrEP users who acquire HIV infection during the study.
- To describe antiretroviral drug resistance among women who acquire HIV infection.

Study Design

This is a single-site sequential multiple assignment randomized trial (SMART) to assess a stepped model of scalable adherence support strategies in young South African women who initiate PrEP.

Women will be consented to have 12 months of follow-up. PrEP will be offered as part of a comprehensive package of sexual and reproductive health care that includes: HIV testing, counseling, condoms, contraception, and testing for and treatment of STIs. Approximately 350 women will be consented and randomized (about 175 participants in each initial intervention arm). Women will receive their assigned interventions until month 9 (the primary endpoint) and will be exited from the SMS and WhatsApp messages at the month-9 visit. They will be followed for an additional three months to assess the intervention's sustained effect on PrEP adherence at month 12.

At enrollment women will be randomly assigned in a 1:1 ratio to receive both standard adherence support counseling with monthly clinic visits and one-way SMS reminder messages and either participation in WhatsApp groups or weekly two-way SMS communication.

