- We will also conduct secondary analyses with PrEP adherence measured as continuous TFV-DP levels and will conduct descriptive summaries of PrEP adherence measured as a five-category variable: BLQ, BLQ-349 fmol/punch, 350-699 fmol/punch, 700-1249 fmol/punch, and ≥ 1250 fmol/punch.

Predictor(s) of interest: Randomized arm (SMS vs. WhatsApp groups; drug level feedback counseling vs. monthly counseling)

Statistical analysis: We will assess the short-term and long-term effects of the intervention on PrEP adherence using the same methods as described for the primary outcome (primary analyses 1 and 2). Shorter term efficacy will be estimated by comparing month 2 TFV-DP levels between primary randomization groups. Longer term efficacy will be estimated by comparing month 12 TFV-DP levels between primary randomization groups and also between secondary randomization groups, among non-responders to the first-line intervention.

Secondary Analysis 2: Create models to estimate the probability of adherence based on sociodemographic factors, individual- and partner-level characteristics, risk practices, and study arm.

Analysis population: All enrolled study participants

Outcome: PrEP adherence the 9-month study visit, defined as a binary outcome variable around TFV-DP levels of 700 fmol/punch

Predictor(s) of interest: Demographics (e.g., age, education), sexual behavior, sexually transmitted infections, perceived risk of HIV, HIV-related stigma, self-efficacy to use PrEP, relationship power dynamics, transactional sex, intimate partner violence, depression, traumatic stress symptoms, alcohol use, treatment arm.

Statistical analyses:

- 1) We will construct risk prediction tools to estimate the probability of adherence at 9 months based on the predictors listed above. We will fit Poisson regression models with all predictors of interest and binary 9-month adherence (TFV-DP ≥ 700 fmol/punch) as the outcome. We will construct two risk prediction tools:
 - i. **Baseline tool:** this model will include all participants, and so will be applicable to the population of AGYW in South Africa. Here, the treatment arm variable will simply be an indicator of SMS/WhatsApp. All predictors will be measured at baseline.

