 - ii. **Non-responder tool:** this model will include those individuals who did not respond to first-line treatment, so it will be generalizable to this subgroup of the population. In this model, the treatment arm variable will be an indicator of DLFB/enhanced counseling. We will also include first-line

treatment. This model will use the most recent values of the predictors of interest (i.e., the most recent available at the time of rerandomization).

- 2) We will evaluate model performance by estimating the area under the receiver operating characteristic curve (AUC) and the calibration intercept and slope. These measures will be adjusted for resubstitution bias via the bootstrap (see Harrell, *Regression Modeling Strategies*).
- 3) There is very little missingness of predictors of interest at baseline. Thus, the first model ("baseline tool") will be based on a complete case analysis, and the second model ("non-responder tool") will be based on last observation carried forward for participants with baseline data available; those without baseline data will be excluded.

Code for risk prediction model fitting and performance assessment

```
library(rms)

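### The SAP's prediction tool for non-responders has no prior-adherence term, although the protocol's objective names one and usable data are held at re-randomization

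*SAP*

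**What the plan says.** **Protocol objective.** Section 2.2 sets a secondary objective: "To identify correlates of PrEP adherence, after adjusting for study arm, such as adherence at prior study visits". The Schema repeats it: "including adherence at prior study visits, sociodemographic factors, individual-level and partner-level characteristics".

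**SAP objective.** The SAP's Study Objectives reword it as "adjusting for study arm, such as sociodemographic factors, individual-level and partner-level characteristics, and risk practices". Prior adherence is gone there and in the SAP Schema, without comment.

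**SAP analysis.** The predictors for Secondary Analysis 2 run from demographics through sexual behaviour and perceived risk to "self-efficacy to use PrEP, relationship power dynamics, transactional sex, intimate partner violence, depression, traumatic stress symptoms, alcohol use, treatment arm". The models are confined to that list: "We will fit Poisson regression models with all predictors of interest and binary 9-month adherence". The non-responder tool adds only the first-line arm. On timing, "This model will use the most recent values of the predictors of interest", meaning the latest available at re-randomization. Missing values in this tool are filled by carrying the last observation forward for women with baseline data.

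**Non-response.** A woman is re-randomized if her TFV-DP is below 500 fmol/punch "or who miss PrEP refills at the month 1 or 2 visits will undergo a secondary 1:1 randomization" (SAP, Study Design).

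**The concern.** The non-responder tool is meant to estimate month-9 adherence at the point of re-randomization. Every woman in it got there because of her recent adherence, yet the model ignores all of that information.

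The study treats the ignored distinctions as meaningful elsewhere:
- The feedback messages in protocol section 4.2.4.2 differ for a detectable level under 500 and for no detectable drug.
- Protocol section 6.4.2 grades adherence in several bands below 700 fmol/punch.
- SAP Primary Analysis 2 tabulates the reasons for re-randomization and may stratify the second-line effect by reason for non-response.

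At stake are the tool's discrimination and the part of the protocol's correlates objective that concerns prior adherence. No treatment comparison is at stake.

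**Working it through.** **1. Where prior adherence appears**

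| Place | Prior adherence named? |
|---|---|
| Protocol Schema, secondary objectives | Yes |
| Protocol 2.2 | Yes |
| Protocol 6.2.2, covariate list | No |
| Protocol 6.4.2, correlates analysis | No |
| SAP Study Objectives and Schema | No |
| SAP Secondary Analysis 2, predictors and both tools | No |

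The gap is between the protocol's objectives and everything downstream of them. The SAP is consistent with itself.

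**2. What is known at re-randomization**

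- *Refill status and reason for non-response:* known for every non-responder, because they define the group. Protocol 4.2.4 has refills checked against electronic pharmacy records.
- *TFV-DP level:* planned for all at month 2 (Appendix IA), but it needs a blood draw. SAP Primary Analysis 2 gives missed visits as an example of a reason for re-randomization, so some women may have no month-2 level. In a public health emergency the classifying sample may come from months 1 to 3 (protocol 4.2.4).

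Using values from before re-randomization creates no leakage, since the outcome is at month 9.

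**3. Size of the non-responder sample**

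Inputs are from protocol Table 2: 175 per first-line arm, 40% response on SMS, and 65%, 60% or 55% on WhatsApp. Non-responders = 175 × (1 − p) + 175 × 0.60:
- p = 0.65: 61.25 + 105 = 166.25 (table: 166)
- p = 0.60: 70 + 105 = 175 (table: 175)
- p = 0.55: 78.75 + 105 = 183.75 (table: 184)

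Table 2 puts month-9 adherence among non-responders at 25% to 50%. The outer limits are 166.25 × 0.25 ≈ 42 and 183.75 × 0.50 ≈ 92 adherent women.

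**4. How informative the level could be (illustration)**

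Assumptions not in the documents: bivariate normal month-2 and month-9 levels with correlation 0.3 to 0.7. Month-2 response was set at 40% to 60%, and month-9 adherence among non-responders at 25% or 40%. Each setting used 400,000 draws. AUC of the month-2 level alone:
- all women: about 0.64 to 0.84
- women below the month-2 cut: about 0.57 to 0.74, because selection on a low level narrows its range
- the same women with 20% to 50% of levels missing and median-filled: about 0.55 to 0.71

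**5. What it adds to the other predictors (illustration)**

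Assumptions: 18 weak other predictors, penalised logistic regression as in the SAP's example code, and selection by low level or missed refill. AUC in new women, without and then with prior adherence:

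| Correlation | Levels missing | n = 120 | n = 175 |
|---|---|---|---|
| 0.5 | none | 0.60 → 0.65 | 0.61 → 0.67 |
| 0.5 | 30% | 0.60 → 0.62 | 0.61 → 0.64 |
| 0.7 | none | 0.62 → 0.73 | 0.63 → 0.76 |

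With correlation 0.3, or with half the levels missing, the gain was at most 0.03.

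A second set of assumptions used 16 weak predictors, 33% adherent, and five added terms (log level, below-quantitation indicator, two refill terms, missing-level indicator). It gave gains of about 0.03 to 0.22 with no missing levels and 0.01 to 0.13 with about a third missing. With a third missing and correlation 0.3 to 0.5, the gain was about 0.01 to 0.05.

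**The case against.** **The SAP follows the protocol's operative text.** Section 6.4.2 describes the correlates analysis as "evaluating demographic, behavioral, perceived risk, stigma, self-efficacy, relationship power, transactional sex, IPV, and alcohol use", and section 6.2.2 does not list prior adherence either. Section 2.2 also introduces its list as examples. This stands: it is a mismatch to reconcile, not an error inside the SAP.

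**A reader might infer that the month-2 level is known for every non-responder.** It is not; only the refill record and the reason for non-response are.

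**A reader might infer that prior adherence is the best predictor and that the tool will discriminate poorly without it.** No figure in the documents supports either claim. Every AUC above rests on assumed correlations, and selection below 500 fmol/punch weakens the level as a predictor. The narrowing is only partial, since a woman with a missed refill qualifies at any level.

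**The extra terms are not free.** With about 42 to 92 adherent women, each term uses information. The SAP's carry-forward rule also does not suit a drug level: PrEP use in the previous 6 months is an exclusion (protocol 3.3.2), so no on-PrEP baseline value exists to carry forward. Both points stand and shape the fix. In the step 5 simulations, adding the terms did not lower mean AUC in any setting.

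**The SAP already looks at reasons for non-response.** It does so descriptively, and perhaps by stratifying Primary Analysis 2. Neither puts the variable into the tool.

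**Conclusion.** The point holds as a cheap improvement. The protocol's objectives name prior adherence, the SAP drops it without explanation, and the non-responder tool omits information that is held at re-randomization and plausibly predictive. The gain in AUC is roughly 0 to 0.1 or more. It depends on the assumed month-2 to month-9 correlation and on the share of missing levels, neither of which the documents give.

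The limits are firm. The baseline tool is rightly left alone, because no on-PrEP adherence exists at enrollment. The randomized first-line, second-line and strategy comparisons are unaffected. A reader might infer that changing this tool answers the protocol's correlates objective. It does not: that objective covers the whole cohort, whereas this covers only women selected for low adherence or missed refills.

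**What to change.** In SAP Secondary Analysis 2, for the non-responder tool only:

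1. Add reason for non-response and month-1 and month-2 refill status, coded so that they do not duplicate each other.
2. Add the latest TFV-DP level from a sample drawn before re-randomization, where measured, for example on the log scale with a below-quantitation indicator. Do not use month-3 levels: Appendix IA schedules that assay only for the drug-level feedback arm.
3. Add a missing-level indicator for the drug level in place of carry-forward.
4. Report optimism-corrected AUC and calibration with and without these terms.
5. Add a sentence reconciling the SAP objective with protocol section 2.2, saying whether prior adherence will be studied as a correlate in the whole cohort. If the terms are left out, give the reason.

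The cost is a few lines of SAP text, no new data collection, and about five terms in a penalised model of modest size.
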